7.3.5. Unscheduled Visits

Unscheduled visits can occur between regularly scheduled visits. For patients who are remaining in Part B (on the OLE) after Visit 8, unscheduled visits may take place as decided by Investigator, but no longer than six months after the prior visit, or prior to exiting the study. Unscheduled Visits assessments will be conducted at the discretion of the PI. These assessments may include vital signs, laboratory testing, etc.

7.4. Screening and Diagnosis

Potential patients will be pre-identified by the site because of a previous TSC diagnosis based on clinical features and/or genetic testing results and those still experience refractory seizures.

7.4.1. Informed Consent/Accent

Procedures specific to this protocol and not otherwise considered standard of care, will not be performed until written informed consent/assent from the parent/caregiver/LAR has been appropriately obtained.

7.4.2. Drug Screen

A drug screen (plasma) will be performed to test for THC and non-approved CBD at Visit 1 (screening). If the screening drug test is positive, a confirmatory retest, via plasma, will be performed after 2 weeks. A positive drug test during the treatment phase will result in early termination.

7.4.3. Demographics and Medical History

Demographics including age, gender, ethnicity and race will be collected. In addition to the genetic evaluation of pathogenic or likely pathogenic *TSC1/TSC2* variant, relevant medical history including but limited to the age of seizure onset, other physical disabilities such as scoliosis, visual impairment, sensory problems and gastrointestinal difficulties will also be assessed. The patient's developmental history will also be assessed. Demographics and Medical History will be reviewed and collected at the Visit 1 (screening). A review of the patient's Medical History will be performed again at Visit 2 (baseline).

7.4.4. Genetic Testing

Genetic testing to assess if the patient has a pathogenic or likely pathogenic *TSC1/TSC2* variant will be conducted by the sponsor's central genetic laboratory if the patient does not have previous genetic testing. Previous genetic testing results are acceptable for review.

Instructions for genetic testing sample collection and processing can be found in the genetic testing laboratory manual.

7.4.5. Seizure Identification and Diagnostic Review

Per the inclusion criteria, enrollment into the study will be based on the presence and frequency of the primary seizure types. The primary seizure types are defined as the following: focal motor seizures without impairment of consciousness or awareness, focal seizures with impairment of consciousness or awareness, focal seizures evolving to bilateral, tonic-clonic convulsive seizures, and generalized motor seizures including tonic-clonic, bilateral tonic, bilateral clonic, or atonic/drop seizures. Focal and generalized nonmotor seizures, infantile or epileptic spasms, and myoclonic seizures do not count as the primary seizure types.

To standardize seizure identification and classification in the study, a SIF/DRF will be submitted and reviewed by the Epilepsy Study Consortium. Approval of the SIF/DRF will be required prior to IP dosing.

Instructions for completion of the SIF/DRF can be found in the Investigator Site File.

7.5. Efficacy Assessments

Efficacy as determined by a reduction in seizures will be evaluated by collecting daily seizure type and frequency in a seizure diary. Days in which no seizures occur will also be noted.

Changes in seizure intensity/duration, CGI-I, as well as changes in behavior and neuropsychiatric symptoms will be assessed by a variety of clinician and caregiver administered instruments.

7.5.1. Seizure Type and Frequency

Parent/caregiver/LAR will record daily seizure frequency denoting seizure type and frequency in a seizure diary. Primary seizure types of focal motor seizures without impairment of consciousness or awareness, focal seizures with impairment of consciousness or awareness, focal seizures evolving to bilateral, tonic-clonic convulsive seizures, and generalized motor seizures including tonic-clonic, bilateral tonic, bilateral clonic, or atonic/drop seizures will be counted towards the primary endpoint.

Patients or parent/caregiver/LAR are to record administration of IP and background AEDs in the daily seizure calendar. Compliance with IP treatment will be assessed by inspecting the patients' diary/seizure calendar and returned supplies with queries as necessary. Patients that fall below 80% compliance at 2 consecutive visits during the maintenance period will not be included in the PP population.

7.5.2. Caregiver Global Impression of Change (CGI-C - Target Behavior)

The CGI-C in Target Behavior is a 7-point Likert scale in which the caregiver chooses one domain from possible domains of sociability, communication, irritability, and hyperactivity to assess change in target behavior after the initiation of IP relative to baseline (prior to treatment with IP). This domain should be chosen based on behavior the parent/caregiver/LAR identifies to be the most impactful. During the baseline visit, the investigator and parent/caregiver/LAR will decide on a domain and identify the specific behavior that the patient exhibits that denotes the domain. This behavior will be used at subsequent visits to assess change after the initiation of IP. The scale ranges from 1- very much improved, 2- much improved, 3- minimally improved, 4- no change, 5- minimally worse, 6- much worse, and 7- very much worse.

[figure not shown]
Caregiver Global Impression of Change - Target Behavior will be assessed at Baseline (Visit 2, Week 0), Visit 4 (Week 5), and Visit 5 (Week 12) in the treatment period (Part A), and will be assessed at Visit 8 (Week 36) and the Final Visit or Taper Visit of the OLE period (Part B).

7.5.3. Clinical Global Impression – Improvement (CGI-I)

The CGI-I is a 7-point Likert scale that the parent/caregiver/LAR and clinician uses to rate the change in overall seizure control, behavior, safety and tolerability after initiation of IP relative to baseline (prior to treatment with IP). The patient will be rated as follows: 1- very much improved, 2- much improved, 3- minimally improved, 4- no change, 5- minimally worse, 6- much worse, and 7- very much worse.

Clinical Global Impression – Improvement (parent/caregiver/LAR and clinician) will be assessed at Baseline (Visit 2, Week 0), Visit 4 (Week 5), and Visit 5 (Week 12) in the treatment period (Part A), and will be assessed at Visit 8 (Week 36) and the Final Visit or Taper Visit of the OLE period (Part B).

7.6. Exploratory Efficacy Assessments

[REDACTED]

[REDACTED]

[REDACTED]

[REDACTED]

[REDACTED]

[REDACTED]

[REDACTED]

7.7. Safety Assessments

Safety will be evaluated by collecting the assessments detailed in the sections below.

7.7.1. Adverse Events

Details regarding AEs and SAEs are provided in Section 8.

7.7.2. Vital Signs

Vital signs including HR (bpm), RR (breaths/minute), body temperature (C/F), BP (mmHg) will be collected at every clinic visit.

7.7.3. Height and Weight

Height will be collected at Visit 1 (screening). Length will be measured if height cannot be obtained. Weight will be collected at Visit 1 (screening), Visit 2 (baseline), Visit 3 (Week 1), and every clinic visit thereafter, including the Final OLE Visit or Taper Visit and Safety Follow-up Post Taper Visit.

7.7.4. Physical/Neurological/Developmental Examinations

The full physical examination will include the following systems:

- General appearance
- Head (eyes, ears, nose and throat)
- Cardiovascular
- Respiratory
- Gastrointestinal
- Genitourinary
- Musculoskeletal
- Endocrine/Metabolic
- Hematologic/lymphatic

IND 044,020
Protocol 1042-TSC-2001

Marinus Pharmaceuticals, Inc.
11 Jun 2021

- Skin
- Other systems as appropriate

The full neurological examination will include:

- Cranial nerves
- Motor exam
- Sensory exam
- Reflexes
- Coordination/Cerebellar

The full developmental examination (applicable only to pediatric patients 2 to 17 years of age, inclusive) will include:

- Speech/language
 - Makes identifiable sounds for specific objects/people
 - Repeats sounds
 - Single words
 - Multiple words
 - Makes a sentence
 - Replies to question in an identifiable sound, single word, multiple word, sentence
 - Other abilities
- Motor
 - Sits with support
 - Sits independently
 - Crawls
 - Stands with support
 - Stands independently
 - Takes steps with assistance
 - Walks independently
 - Other abilities
- Social
 - Smiles appropriately to situation
 - Makes eye contact

7.7.5. ECG

Electrocardiograms will be performed to collect the electrical activity of the heart throughout the study to monitor safety. An evaluation of normal by a physician must be obtained before the patient is enrolled in the treatment period.

Electrocardiograms will be performed at Visit 2 (baseline), Visit 3 (Week 1), Visit 4 (Week 5), and Visit 5 (Week 12) in the treatment period (Part A), and will be assessed at Visit 7 (Week 28) and the Final OLE Visit or Taper Visit in the OLE period (Part B).

7.7.6. Clinical Laboratory Tests

Laboratory safety assessments will be collected at every clinic visit throughout the study to monitor patient safety. Clinical laboratory tests are listed in Section 12.2 will be collected per the schedule listed in Table 1 and Table 2. These clinical laboratory assessments will include complete blood count with automated differential, creatinine, blood urea nitrogen, and eGFR calculation, comprehensive metabolic panel, as well serum pregnancy test for all girls/women of childbearing potential. Local laboratories will be utilized by the sites.

The following liver function and eGFR tests will be monitored throughout the study as follows.

- If AST or ALT increases > 3 times ULN during the study, patient should be followed with weekly laboratory repeat testing and continue in study if levels trending down. Patient will be discontinued if levels do not decline to under $3 \times$ ULN.
- If total bilirubin increases to $1.5 \times$ ULN or more during study, the patient will be discontinued.
- Patients with significant renal insufficiency, eGFR < 30 mL/min (calculated using the Cockcroft-Gault formula), will be discontinued if the criterion is met post baseline.

If any of the criteria above are deemed clinically significant by the investigator, then the sponsor's medical monitor should be contacted.

Urinalysis will be conducted at Visit 1 (screening) or Visit 2 (baseline), Visit 3 (Week 1), Visit 4 (Week 5), and Visit 5 (Week 12) in the treatment period (Part A), and Visit 7 (Week 28), Visit 8 (Week 36), the Final Visit or Taper Visit, and the Safety Follow-up or Post Taper Visit in the OLE period (Part B).

An attempt will be made to collect a urine sample at screening in order to perform the study-related urinalysis. Otherwise, the urine sample for the urinalysis can be collected at baseline.

7.7.7. Tanner Staging

The Tanner scale (also known as the Tanner stages) is a scale of physical development in children, adolescents and adults. The scale defines physical measurements of development based on external primary and secondary sex characteristics. Patients will be evaluated and rated as Tanner I, Tanner II, Tanner III, Tanner IV, and Tanner V. Tanner staging will occur at Visit 1 (screening) and Visit 5a (only for patients who do not continue into Part B) of the treatment period (Part A), and at the Final OLE Visit or Taper Visit (Part B).

7.7.8. Investigational Product PK

Please refer to Section 7.8 for additional details regarding PK assessments.

7.7.9. Concomitant AED Levels

Concomitant AED levels are not mandatory but will be collected per sites' standard of care. If AED levels are available for Visit 1 (screening), Visit 2 (baseline), Visit 3 (Week 1), Visit 4 (Week 5) and Visit 5 (Week 12), and throughout the OLE period of the study at the time points noted in Table 1 and Table 2, the results, date and time of last AED dose and date and time of AED PK sample will be recorded in the eCRF.

7.8. Pharmacokinetic Assessments

Blood sampling for PK evaluation must be performed at the precise protocol scheduled time. Actual sampling time(s) must be accurately recorded in the source document and appropriate eCRF.

One blood sample will be obtained at Visit 4 (Week 5), and Visit 5 (Week 12) in the treatment period (Part A), and at Visit 6 (Week 20), Visit 7 (Week 28), Visit 8 (Week 36), Final OLE Visit or Taper Visit, and Safety Follow-up Post Taper Visit of the OLE period (Part B).

A population PK approach addressing the relationship between GNX PK parameters and individual characteristics will be implemented at Visit 4 (Week 5) and Visit 5 (Week 12) in the treatment period.

During Part A:

- Visit 4 (Week 5): between 1 and 5 hours since the last IP dosing.
- Visit 5 (Week 12): between 4 and 8 hours since the last IP dosing.

During Part B:

There is no specified time to draw the PK sample and can be drawn when convenient during the study visit. Exact time of sample withdrawal and IP intake will be recorded in the eCRF.

7.8.1. Clinical Pharmacokinetic Blood Sample Collection and Handling Procedures

Pharmacokinetic blood collection must not deviate from the nominal collection time set forth in the protocol by more than \pm 30 minutes from samples drawn within 4 hours post-dose or by more than \pm 60 minutes for samples drawn beyond 4 hours post-dose. Samples drawn outside these parameters will be considered a protocol deviation.

Please refer to the laboratory manual for processing instructions.

8. ADVERSE AND SERIOUS ADVERSE EVENT ASSESSMENTS

8.1. Definition of Adverse Events, Period of Observation, Recording of Adverse Events

An AE is any untoward medical occurrence in a clinical investigation patient who has been administered a pharmaceutical product; it does not necessarily have a causal relationship with this treatment. An AE can therefore be any unfavorable and unintended sign (including an abnormal laboratory finding), symptom, or disease temporally associated with the use of a medicinal (investigational) product, whether or not related to the medicinal (investigational) product (International Council for Harmonisation [ICH] Guidance E2A March 1995).

All AEs are collected from the time the informed consent/assent is signed until the defined follow-up period. This includes events occurring during the screening period of the study, regardless of whether or not the IP has been administered. All AEs reported after the initiation of IP will be considered treatment-emergent AEs. Where possible, a diagnosis rather than a list of symptoms should be recorded. If a diagnosis has not been made, then each symptom should be listed individually. All AEs should be captured on the appropriate AE pages in the eCRF and in source documents. In addition to untoward AEs, unexpected benefits outside the IP indication should also be captured on the AE eCRF page.

All AEs must be followed to closure (the patient's health has returned to baseline status or all variables have returned to normal), regardless of whether the patient is still participating in the study. Closure indicates that an outcome is reached, stabilization is achieved (the investigator does not expect any further improvement or worsening of the event), or the event is otherwise explained. When appropriate, medical tests and examinations are performed so that resolution of event(s) can be documented.

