8.1.1. Severity Categorization

The severity of AEs must be recorded during the course of the event, including the start and stop dates for each change in severity. An event that changes in severity should be captured as a new event. Worsening of pretreatment events, after initiation of the IP, must be recorded as new AEs (e.g., if a patient experiences mild intermittent dyspepsia prior to dosing of the IP, but the dyspepsia becomes severe and more frequent after the first dose of the IP has been administered, a new AE of severe dyspepsia [with the appropriate date of onset] is recorded on the appropriate eCRF page).

The medical assessment of severity is determined by using the following definitions:

Mild: A type of AE that is usually transient and may require only minimal treatment or therapeutic intervention. The event does not generally interfere with usual activities of daily living.

Moderate: A type of AE that is usually alleviated with specific therapeutic intervention. The event interferes with usual activities of daily living, causing discomfort, but poses no significant or permanent risk of harm to the research patient.

Severe: A type of AE that interrupts usual activities of daily living, that significantly affects clinical status, or that may require intensive therapeutic intervention.

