8.2.4. Serious Adverse Event Collection Time Frame

All SAEs (regardless of relationship to study) are collected from the time the parent/caregiver/LAR signs the informed consent/assent until the defined follow-up period stated and must be reported to the Marinus Safety Department *and* the CRO/Marinus medical monitor within 24 hours of the first awareness of the event.

In addition, any SAE considered “related” to the IP and discovered by the investigator at any interval after the study has completed must be reported to the Marinus Safety Department within 24 hours of the first awareness of the event.

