4.3.2 Adverse Events

Adverse events (AEs) are collected from the time of informed consent/assent through the defined follow-up period. AEs are coded using MedDRA dictionary, version 22.0 and are categorized by system organ class (SOC) and preferred term (PT). A treatment-emergent AE (TEAE) is defined as an AE that starts or worsens on or after the first day of dosing with IP. Analyses of TEAEs for Part A of the study will include AEs that start or worsen during Part A and will not include any AE that starts or worsens during Part B. For Part B of the study, TEAEs will be include events that start or worsen after the first day of Part B relative to the first day of Part B. TEAEs over the entire study will be summarized for patients who participate in both Parts A and B of the study.

Tabulations of AEs will be by patient such that an individual is only counted once per summary category. Detailed by-patient listings of all AEs reported during the study will be provided and will include verbatim and coded terms for each AE.

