4.3.2.5 Serious Adverse Events (SAEs)

The number and percentage of patients reporting at least one AE that meets with criteria for an SAE will be summarized by MedDRA SOC and PT. A similar summary of SAEs reported as related to study drug will be presented. The seriousness reason will be provided in the by-patient SAE listing.

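### The SAP's SAE rows are not limited to treatment-emergent events, so pre-dose SAEs enter the reported SAE rate; eased events and recorded benefits may also reach the TEAE tables

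*Protocol*

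**What the plan says.** **Collection.** Protocol 8.1 begins "An AE is any untoward medical occurrence in a clinical investigation patient who has been administered a pharmaceutical product". It then starts AE collection at consent and adds: "This includes events occurring during the screening period of the study, regardless of whether or not the IP has been administered". For serious events, Protocol 8.2.4 says "All SAEs (regardless of relationship to study) are collected from the time" consent or assent is signed. Protocol 3.1 and SAP 1.3.1 place the 4-week baseline inside Part A, and SAP 3.1.1 lets it run from 28 to 32 days.

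**SAE tables.** The overview in SAP 4.3.2.1 has six rows. Five concern TEAEs: any, related, leading to discontinuation, by worst severity, and fatal. The remaining row is for any SAE. SAP 4.3.2.5 tabulates "The number and percentage of patients reporting at least one AE that meets with criteria for an SAE" by SOC and PT, with a matching table for related SAEs. Neither section sets an onset limit. SAP 2.2 and 4.3 base the safety tables on dosed patients and report Part A, Part B and both parts together.

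**Treatment emergence.** Protocol 8.1: "All AEs reported after the initiation of IP will be considered treatment-emergent AEs". SAP 4.3.2: "A treatment-emergent AE (TEAE) is defined as an AE that starts or worsens on or after the first day of dosing with IP". For Part B, the SAP moves the reference point to the first day of Part B.

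**Recording rules.** Protocol 8.1.1: "An event that changes in severity should be captured as a new event". It asks for start and stop dates at each change and names no direction. Protocol 8.1 also states: "In addition to untoward AEs, unexpected benefits outside the IP indication should also be captured on the AE eCRF page". Neither document describes a flag for benefit records, a rule that keeps them out of the tables, or a link between a severity-change record and the event it came from.

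**The concern.** Preliminary safety is part of the primary objective (Protocol 2.2.1), and long-term safety in Part B is a secondary objective (Protocol 2.2.2). The trial has one open-label arm and plans about 30 dosed patients. No control group shares the same counting errors, so the percentages will be read as what happened on ganaxolone.

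An SAE row placed among five TEAE rows invites that reading, yet it also covers weeks in which nobody had taken the drug. The recording rules raise a related worry. If an eased event gets a new record with a new start date, or a benefit sits on the AE page without a marker, a program that selects on start date alone can tabulate it as treatment-emergent.

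**Working it through.** The plan states no SAE rate or expected event count, so there is no figure of its own to reproduce. The check applies the counting rules as written.

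**1. Pre-dose SAEs.** Take a patient with an unplanned hospital admission in the baseline period who is dosed afterwards.

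- The event is collected (Protocol 8.1, 8.2.4).
- The patient is in the Safety population (SAP 2.2).
- The event falls in Part A (Protocol 3.1).
- The any-SAE row and the 4.3.2.5 table have no onset condition, so the patient is counted.
- The starts-or-worsens condition in SAP 4.3.2 governs TEAEs only and does not remove the event.

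SAEs of screen failures are not counted, because those patients are never dosed.

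**2. Size.**

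- One patient: 1/30 = 3.3 percentage points.
- Pre-dose share of baseline plus 12 weeks (84 days) of treatment: 28/(28+84) = 25.0%; 32/(32+84) = 27.6%.
- If 4 weeks of taper and follow-up are added (112 days): 28/140 = 20.0%; 32/144 = 22.2%.

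These are shares of time, not of events. To translate them, **assume** a constant SAE rate r per patient per 28 days, the same before and after dosing. Expected patients with at least one SAE are 30 × (1 − exp(−r × days/28)), using 84 days for treatment-emergent SAEs and 112 or 116 days for all SAEs.

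| Assumed r | Treatment-emergent | All SAEs | Excess patients |
|---|---|---|---|
| 0.01 | 0.89 | 1.18–1.22 | 0.29–0.33 |
| 0.03 | 2.58 | 3.39–3.51 | 0.81–0.92 |
| 0.05 | 4.18 | 5.44–5.61 | 1.26–1.43 |
| 0.10 | 7.78 | 9.89–10.18 | 2.11–2.40 |

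Across this tenfold range the excess is about 0.3 to 2.4 of 30 patients, or 1 to 8 percentage points (0.29/30 and 2.40/30).

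**3. Severity decreases.** Three constructed patients show where the rule matters.

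- *Starts on treatment, eases in the same part.* There are two records, but SAP 4.3.2 counts a patient once per category and 4.3.2.3 uses the worst severity. Nothing is added.
- *Starts before dosing, eases after first dose.* The new record starts on treatment. Selection on start date adds a Part A TEAE.
- *Starts in Part A, eases in Part B.* The new record starts in Part B. The parts are tabulated separately, so counting once per patient does not help, and selection on start date adds a Part B TEAE.

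**4. Benefits.** A benefit recorded after dosing reaches a TEAE table only if every row on the AE page is treated as an AE. If it were, and its severity and relationship fields were blank, the defaults in SAP 4.3.2.3 and 4.3.2.4 would show it as severe and related.

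**The case against.** **On SAEs.** The row does what its label says, and Part A does include baseline. Onset dates are in the listings, the death and discontinuation rows are limited to TEAEs, and related SAEs have their own table. A missing relationship is set to related only for events on or after dosing. Protocol 8.2.3 also removes previously scheduled admissions for conditions that have not worsened. One could add that Protocol 8.1 defines an AE in a patient who has received a product; but the same section expressly brings in screening events. These points limit the harm. They do not change what the headline percentage contains, and a reader should not need a listing to correct it.

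**On severity.** SAP 4.3.2 asks whether an event starts or worsens and, for Part B, relative to the first day of that part. An event that goes from moderate to mild has done neither; only a record has started. The worked example in Protocol 8.1.1 is also about worsening. This is a good argument about intent, and it stands. The gap is that the protocol calls the change a new event and the SAP does not say how to treat it.

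**On benefits.** A reader might infer that the safety tables in general count improvements and benefits against ganaxolone, and that the TEAE and related-TEAE rates would therefore be overstated. The documents do not support that. AEs are defined as untoward and benefits are recorded in addition to them, so by definition a benefit is not a TEAE. The eCRF is not among the documents, and the programming specifications and table templates are separate (SAP 7 and 8), so an exclusion may exist there.

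**Conclusion.** The SAE point holds on the text. The any-SAE row and the SAE table by SOC and PT count pre-dose SAEs of patients who are later dosed, at 3.3 percentage points per patient with 30 dosed. The total excess is unknown because the documents give no SAE rate. The 0.3 to 2.4 patients above rest wholly on the assumed rates and on those rates being equal before and after dosing.

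The severity point is an ambiguity confined to two cases: a pre-dose AE that eases after first dose, and a Part A AE that eases in Part B. In Part B one patient is 6.7 points if 15 enter (1/15; the 15 is assumed) and at least 3.3 points if no more than 30 do. The benefits point is an unhandled gap, not a stated miscount. Neither supports a claim that TEAE rates will be inflated; they show only that the plan does not rule it out.

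**What to change.** SAP wording is sufficient.

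- **4.3.2.1 and 4.3.2.5:** tabulate treatment-emergent SAEs, including the related-SAE table, by part and overall. List pre-dose SAEs separately. Date them by SAE onset as Protocol 8.2.5 defines it, so that an event which begins before dosing but becomes serious on treatment is still counted.
- **4.3.2, severity:** state that a record opened only because severity decreased continues the earlier event and is not a new TEAE in that period.
- **4.3.2, benefits:** state that benefit records are excluded from the TEAE tables, and how they will be identified. Review of verbatim terms before database lock would do this without an eCRF change.
- **4.3.2, definition:** say that the SAP's starts-or-worsens rule governs the tables, since Protocol 8.1 words treatment emergence by when an event is reported.

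All records stay in the listings, so no information is lost. The cost is a few sentences, slightly more programming, and matching severity-change records to their parent events.
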